10.3 Magnetic Resonance Imaging

Participants will be imaged using a Siemens Trio 3T MRI scanner with 32 channel head coil using a magnetization prepared rapid gradient echo (MPRAGE) acquisition with isotropic image resolution of 1.0 mm and full head field of view. Imaging will be performed in the sagittal plane with repetition of sequences deemed at the time of acquisition to exhibit patient head motion or other artifacts. Images will be analyzed using SPM12 toolbox for MATLAB, with linear normalization to Montreal Neurological Institute (MNI) template brain space, segmentation of gray matter, white matter, CSF, and volumetric quantitation of gray matter voxels and gray matter density compared to previously acquired control cohorts using the same sequence, with age-matched normative database. Regions of abnormal volume and density will be identified in 116 regions of the automated anatomical labeling (AAL) brain atlas.

10.4 Data Analysis

The primary hypothesis is that individuals with chemotherapy induced cognitive impairment (CICI) will have a greater than expected amyloid plaque burden when compared to a control group of individuals who are not experiencing cognitive complaints. It is hypothesized that increased and abnormal [¹⁸F]Flutemetamol uptake will be present in individuals with CICI. The primary analysis will be an exact one sample binomial test based on a composite SUVR of 0.59 (Z-score =2) provided by the CortexID software from GE Healthcare. A Z-score greater than or equal to 2.0 (composite SUVR greater than or equal to 0.59) will be coded as a positive amyloid scan and a Z score less than 2.0 (composite SUVR less than 0.59)¹³⁴ will be coded as negative. In clinical practice visual analysis is the standard approach for assessing amyloid positivity. This provides a simple binary positive or negative visual assessment of flutemetamol uptake. Since the visual approach is the standard used in clinical interpretation (Vizamyl prescribing information - section 2.5)¹ we will also perform a secondary visual analysis to compare with the more quantitative SUVR approach to assess for correlation between the composite SUVR and visual binary analysis methods. This is an exploratory analysis independent from the primary binary determination of amyloid positivity based on the composite SUVR. The prevalence of amyloid plaque burden in cognitively normal elderly individuals is up to 33% depending on the amyloid imaging agent used, patient age, and criteria used for evaluation.^{1,142-145} However, using [¹⁸F]Flutemetamol in a slightly younger population, Vandenberghe al. found that in a group of fifteen cognitively intact healthy volunteers over 55 (mean age 68.7) only one healthy volunteer had a positive amyloid scan.¹²³

The following exploratory endpoints will also be also evaluated:

- I. Objective cognitive impairment correlated with subjective reports of cognitive impairment as measured by administered questionnaires.
- II. Amyloid plaque burden using regional semi-quantitative determinations is associated with greater objective cognitive impairment.
- III. Those individuals with the most profound cognitive impairment may have associated regional FDG metabolic changes consistent with neuronal loss or damage.

The imaging parameters will include the Z score values from Cortex ID for FDG and Z scores, regional SUV values and the composite SUVR for [¹⁸F]lutemetamol from CortexID.¹⁴⁶ For FDG these particular values are in comparison to an age-matched cohort so by definition they define a degree of FDG uptake reduction from normal. For [¹⁸F]Flutemetamol there is no specific age-related deposition in the database to assess age-matched normality so the study images will be compared the database control group as a whole to determine the Z scores compared to clinically negative amyloid scans. Z score values both regional and global for FDG and composite ([¹⁸F]Flutemetamol) can then be correlated with the various neuropsychological variables and clinical variables obtained to assess for differences and trends. The data will be analyzed descriptively using summary statistics and paired t-tests. Means, standard deviations and confidence intervals will also be reported. Scatterplots and bivariate summaries such as Pearson correlation coefficient and scatterplots will be used to characterize pairs of imaging parameters.

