7.3 Primary Endpoint

Our primary hypothesis is that individuals with chemotherapy induced cognitive impairment will have a greater than expected amyloid plaque burden when compared to a control group of individuals who are not experiencing cognitive complaints. The chemotherapy may accelerate the process of amyloid plaque burden deposition and subsequent possible neuronal injury and loss in individuals who have undergone CICI. The primary endpoint will be amyloid plaque burden assessed by visual criteria as outlined in the recently approved Vizamyl (flutemetamol F 18 injection) prescribing information.¹ This will be a binary assessment of the images being positive or negative by visual criteria for abnormal [¹⁸F]Flutemetamol uptake. A secondary analysis of [¹⁸F]Flutemetamol binding will occur using a regional semi-quantitative technique as described by Vanderberghe et al.¹²³ and Thufjell et al¹³⁴.

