The primary assessment of amyloid plaque burden will be with visual assessment of abnormal cortical flutemetamol uptake as outlined in the recently approved Vizamyl (flutemetamol F 18 injection) prescribing information (section 2.5).¹ This will be a binary assessment of the images being positive or negative for increased and abnormal flutemetamol uptake and thus increased amyloid plaque burden. A secondary analysis of flutemetamol binding will occur using a regional semi-quantitative technique as described by Vanderberghe et al.¹²³ In this technique, a semi-quantitative global composite of standardized uptake value ratios (SUVRs) in the cerebral cortex which is obtained and normalized to the cerebellum or pons. The following regions are averaged to yield the global composite: lateral frontal, lateral temporal, lateral parietal, anterior cingulate, and posterior cingulate. This will yield a global composite for [¹⁸F]Flutemetamol-PET data. GE proprietary software (CortexID Suite) is available in our laboratory and will be used to determine both regional SUV values and a composite SUVR for [¹⁸F]Flutemetamol uptake. This database also contains [¹⁸F]Flutemetamol scan data from 105 healthy volunteers and has been validated to be over 99% concordant with visual reads using 172 scans from AD, MCI, and healthy controls using a threshold Z score of 2 (which corresponds to a composite SUVR of 0.59). This software will provide the control population to which we will compare our symptomatic CICI patients. Z scores obtained for the study patients using this software will then be correlated with available clinical data, neuropsychological data, and the regional FDG Z scores or metabolic rates.

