10.5 Justification of Sample Size

Twelve evaluable patients (defined as having complete imaging and blood data available) will be enrolled in this study. By definition, 100% of evaluable patients enrolled will receive the complete set of PET studies [¹⁸F]Flutemetamol, FDG, and MRI. Due to blood drawing issues the total enrollment will need to be approximately 15 subjects to assure that complete blood and imaging data sets in 12 participants will be available for analysis. The data from Vandenberghe al. found that in a group of fifteen cognitively intact healthy volunteers over 55 (mean age 68.7) only one healthy volunteer had a positive amyloid scan.¹²³ Based on this data using a population similar in age to the expected experimental cohort, our null hypothesis (H_0) is that 12% of study participants will have amyloid positivity. With 12 patients we will have 80% power to reject H_0 at the nominal 0.05 one-sided significance level provided the true proportion of subjects with amyloid positivity is 42%. The null hypothesis will be rejected if 4 or more out of 12 patients show amyloid positivity. We will not image a separate control population in this study. The CortexID software contains a database of [¹⁸F]Flutemetamol scan data from 105 healthy volunteers¹³⁴ and will serve the function of a control group for the purposes of this exploratory study. The CortexID database has been validated in a subsequent study using [¹⁸F]Flutemetamol scans from 345 AD, MCI, or cognitively normal individuals.¹³⁴

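### The exploratory check of SUVR against the visual read is planned as a correlation, which does not show whether the two binary calls agree at 0.59 or give the same 4-of-12 answer

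*Combined protocol and SAP*

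**What the plan says.** Section 10.4 defines the primary test: "The primary analysis will be an exact one sample binomial test based on a composite SUVR of 0.59". A scan with a composite SUVR of 0.59 or more (Z of 2.0 or more) counts as positive. The same section adds a visual positive/negative read, because that is the clinical standard, and gives its purpose as "to assess for correlation between the composite SUVR and visual binary analysis methods". It then sets the status of that comparison: "This is an exploratory analysis independent from the primary binary determination of amyloid positivity based on the composite SUVR". Later in 10.4, "bivariate summaries such as Pearson correlation coefficient and scatterplots will be used to characterize pairs of imaging parameters".

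Section 10.5 gives the decision rule without saying which read feeds it: "The null hypothesis will be rejected if 4 or more out of 12 patients show amyloid positivity".

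Two other sections rank the reads the other way round. Section 7.3 says "The primary endpoint will be amyloid plaque burden assessed by visual criteria", and section 10.2 says "The primary assessment of amyloid plaque burden will be with visual assessment of abnormal cortical flutemetamol uptake". Section 10.2 also reports that the software cut-off was over 99% concordant with visual reads in 172 external scans, and it leaves the SUVR reference region open between two choices (cerebellum or pons).

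For the study patients, the plan has no 2x2 table, percent agreement, kappa, listing of discordant scans, or repeat of the 4-of-12 rule on the visual read.

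**The concern.** Two methods that each label a patient positive or negative should be compared on whether they label the same patients the same way. Correlation answers a different question: whether SUVR tends to be higher in visually positive patients. Adding a constant to every SUVR, or rescaling them all, leaves the correlation unchanged but can move patients across 0.59. The open choice of reference region is one place in the protocol where such a shift could arise.

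With 12 patients and a rejection limit of 4, one discordant scan can separate the two reads' answers. A high coefficient could then be reported as support for the SUVR call when the clinical-standard read would have given the opposite conclusion. This would be a side issue if the SUVR call were primary throughout the protocol, but sections 7.3 and 10.2 give that place to the visual read.

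**Working it through.** **Inputs from the plan.** Sections 10.4 and 10.5: n = 12 evaluable; null rate 12%; alternative 42%; one-sided 0.05; reject at 4 or more; SUVR cut-off 0.59. Section 10.2: external concordance over 99%. All individual SUVRs below are constructed for illustration; none comes from the documents.

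**1. Reproduce the design.** Exact binomial:
- P(X ≥ 4 | 12, 0.12) = 0.046, within the nominal 0.05.
- P(X ≥ 4 | 12, 0.42) = 0.815, against the stated 80%.
- A limit of 3 would give P(X ≥ 3 | 12, 0.12) = 0.167.

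The plan's figures reproduce, and 4 is the smallest valid limit.

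**2. Continuous SUVR against the 0/1 visual read.** Take SUVRs 0.45, 0.47, 0.49, 0.50, 0.52, 0.53, 0.55, 0.60, 0.62 (visually negative) and 0.85, 0.90, 0.95 (visually positive). The Pearson coefficient with a 0/1 variable is

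r = (mean of positives − mean of negatives) / SD × √(p(1 − p))

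= (0.900 − 0.5256) / 0.1699 × √(0.25 × 0.75) = 0.954, with the SD computed on divisor 12.

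SUVR positives: 5 of 12, reject. Visual positives: 3 of 12, do not reject.

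Now subtract 0.05 from every SUVR. The values 0.60 and 0.62 become 0.55 and 0.57, so SUVR positives fall to 3 and the two reads agree on all 12 patients. The coefficient is still 0.954. The same statistic describes both full agreement and opposite conclusions.

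A more extreme case: 8 visual negatives evenly spaced over 0.39–0.41 and 4 visual positives evenly spaced over 0.56–0.58 give r = 0.996, with SUVR 0 of 12 and visual 4 of 12.

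**3. Both calls made binary first.** For a 2x2 table with a = both positive, b = SUVR only, c = visual only, d = both negative,

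phi = (ad − bc) / √[(a+b)(c+d)(a+c)(b+d)].

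- First example in step 2 (a, b, c, d = 3, 2, 0, 7): phi = 21/√(5×7×3×9) = 0.683. Agreement is 10/12, exact 95% interval 52% to 98%. Chance agreement is (5×3 + 7×9)/144 = 0.542, so kappa = (0.833 − 0.542)/(1 − 0.542) = 0.64.
- Over every 12-patient table in which the reads fall on opposite sides of the rule, the largest phi is at (3, 1, 0, 8) or its mirror image: 24/√(4×8×3×9) = 0.816. Agreement is 11/12. Chance agreement is (4×3 + 8×9)/144 = 0.583, so kappa = (0.917 − 0.583)/(1 − 0.583) = 0.80.

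**4. When the coefficient does not exist.** If no scan is visually positive, the visual variable is constant and r is undefined. At the null rate this has probability 0.88^12 = 0.216; at the alternative rate it is 0.58^12 = 0.001.

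**5. How often the reads would give opposite answers.** Assume each visual call matches the SUVR call with a fixed probability, errors are independent, and SUVR positivity lies between 12% and 42%. Summing the exact probabilities over all combinations:

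| Per-scan concordance | Opposite 4-of-12 answers |
|---|---|
| 99% | 1.3% to 3.0% |
| 95% | 7% to 13% |
| 90% | 12% to 23% |

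The 99% row approximates the external figure. The other two rows are assumptions that show the sensitivity.

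**The case against.** **The word may be loose.** Section 10.4 names no coefficient for this comparison. Its phrase refers to binary methods, and section 10.2 speaks of concordance for the same pair of reads. Pearson is only an example in 10.4, offered for imaging parameters among which the visual read is not listed. This stands as a reading. A reader might infer that a near-perfect correlation between the two binary calls could hide opposite conclusions; the arithmetic does not support that, since the ceiling is 0.816. Values of 0.95 and above need the continuous SUVR. On either reading the plan should state the measure.

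**It cannot change the result.** Under section 10.4 only the SUVR call enters the binomial test, so a reader who infers that one or two discordant reads would decide the trial goes beyond that section. This stands for 10.4 alone. It is weakened by sections 7.3 and 10.2.

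**Disagreement is unlikely.** The external concordance is over 99%, and at that level opposite answers occur about 1% to 3% of the time. This stands as a statement of likelihood if the figure carries over. But those 172 scans came from people with Alzheimer's disease or mild cognitive impairment and healthy controls, not from women treated with chemotherapy. A correlation in this study would not give a figure to set beside it.

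**Scatterplots are planned.** If they include SUVR against the visual read, 12 points would show each discordant scan. That is a real mitigation, but the plan does not say this plot will be made or that the decision will be compared.

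**Agreement measures have gaps too.** With no positives on either read, positive agreement is 0/0, and kappa of 0.80 is compatible with opposite answers. Both points stand and shape the fix. Overall and negative agreement remain available. It would also be wrong to extend the uncomputable case to the 56.9% chance of at most one positive, because a correlation exists with exactly one.

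**Conclusion.** The point holds as a defect in an exploratory analysis. Read literally, the planned correlation does not register where 0.59 falls: it can be 0.95 or higher while the two reads give opposite answers to the 4-of-12 rule. Read as a correlation of two binary calls, it can still be 0.82 in that situation. At the 12% null there is a 21.6% chance that it cannot be computed at all.

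The documents do not show that opposite answers are likely. That depends on per-scan concordance in this population, which is untested, and on the assumption of independent errors. Nor does the defect affect the validity of the SUVR test as 10.4 defines it. What raises it above a wording matter is that the protocol disagrees with itself about which read is primary. Until that is settled, whether both reads lead to the same decision is the most useful thing this comparison can report.

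**What to change.** In section 10.4, replace correlation with agreement of the two binary calls, and report:

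- the 2x2 table of SUVR at or above 0.59 by visual read;
- overall agreement with an exact 95% interval, and positive and negative agreement where they are defined;
- a listing of each discordant patient with her composite SUVR;
- the 4-of-12 decision under each read, with a statement of whether it is the same.

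An agreement coefficient alone is not enough, because a single discordant scan can flip the rule; the last two items cover that. A plot of SUVR by visual read with a line at 0.59 would be a helpful addition.

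Separately, reconcile sections 7.3 and 10.2 with 10.4 on which read is primary, and say in 10.5 which read the rule uses.

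The cost is one or two sentences and one small table, from reads already planned. The change should be made before the data are analysed.

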8.3 Inclusion Criteria

- Female patients must be 18 years or older for inclusion in this research study. There is inadequate experience with the safety of [¹⁸F]Flutemetamol in children and therefore this radiopharmaceutical should not be used in patients under the age of 18. Individuals over 70 years age will be excluded as the incidence of amyloid positivity increases significantly even with no cognitive problems and will not allow for testing of our primary hypothesis.
- The patient must have a histologically proven diagnosis of Stage I through IIIC Breast Cancer.
- The patient must have completed adjuvant chemotherapy more than 6 months ago, but no more than 36 months prior to initial study scan.
- The patient must report persistent cognitive problems following the initiation of chemotherapy, defined as being one or more standard deviations above normative data on our two scales of subjective cognitive dysfunction. This is defined as a total score of 45 or higher on the Cognitive Failure Questionnaire, and a T-score of 60 or higher on the Frontal System Behavioral Scale Questionnaire.
- Patients must agree to have clinical and radiographic endpoints and the results of histopathologic tissue analysis and other laboratory information entered into a research database, as evidenced by signing the informed consent form.
- All patients, or their legal guardians, must sign a written informed consent and HIPAA authorization in accordance with institutional guidelines.

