9.3 Neuropsychological Exams

To assess memory, we will utilize the Hopkins Verbal Learning Test – Revised (HVLT-R) and the Brief Visuospatial Memory Test – Revised (BVMT-R). Processing speed will be tapped with Trail Making Test Part A (TMT-A) and the Coding and Symbol Search subtests of the Wechsler Adult Intelligence Scale – IV. Executive functioning will be measured with Trail Making Test Part B (TMT-B), Controlled Oral Word Association Test (COWAT), and Stroop Color Word Test (SCWT). Additionally, the Wide Range Achievement Test (WRAT4) will be used to assess premorbid intellect in all participants.

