APPENDIX D: Schedule of Events

Test / Procedure	Screen	Research MRI study and Neuro-psychological Testing	PET Imaging Visit 1 First PET Exam Will depend on whether [¹⁸ F]-Flutemetamol or FDG study is performed	PET Imaging Visit 2 Second PET Exam Will depend on whether [¹⁸ F]-Flutemetamol or FDG study is performed
Inclusion / Exclusion Criteria	X			
Informed Consent	X			
Research MRI study		X		
Infusion of [¹⁸ F]Flutemetamol			X	X
[¹⁸ F]Flutemetamol PET Imaging			X	X
Adverse Event Questionnaire After [¹⁸ F]Flutemetamol study			X (3)*	X (3)*
¹⁸ F-FDG PET Imaging			X	X
Neuropsychological Testing		X		
Pregnancy Test (1)			X (2)	X (2)

* Performed immediately after [¹⁸F]Flutemetamol study

1 Patient must be postmenopausal for a minimum of one year, surgically sterile, or has been confirmed not to be pregnant by serum pregnancy test performed within 48 hours prior to research PET imaging.

2 GE requires all pregnancies that occur within 30 days of exposure to the investigational product be submitted to their institution. Patients will be contacted approximately 30 days post [¹⁸F]Flutemetamol scanning to collect information from the patient regarding pregnancy status.

3 A follow-up telephone call will be made to each participant within 1 day following their imaging scan with [¹⁸F]Flutemetamol. If the participant cannot be contacted at 1 day post-scanning, then we will continue trying to contact them for up to 7 days post-scanning.

4 The research MRI study and neuropsychological testing can be completed depending on staff availability and can be done before, after, or in between PET/CT imaging sessions.

Research MRI study

The research MRI study will include the following imaging sequences/studies. This is our current clinical brain tumor imaging protocol.

Scout

T1-weighted SE (pre injection)

T2

FLAIR;

Dynamic contrast enhanced images with associated T1 mapping

Diffusion- weighted imaging

Post T1-weighted SE

PET Imaging Visits 1 & 2:

Imaging of the PET tracers will be performed on two separate days with FDG imaging occurring on one day and [¹⁸F]Flutemetamol occurring on another day. The imaging will be performed on separate days depending on scheduling with the cyclotron. The days of imaging will be scheduled according to scanner and cyclotron availability, and all days of imaging will be obtained within six weeks of each other.

APPENDIX E: [¹⁸F]Flutemetamol Patient Adverse Event QuestionnaireCompleted at conclusion of [¹⁸F]Flutemetamol infusion.

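### Exploratory endpoints II and III relate imaging to one post-chemotherapy level of cognition, with no stated adjustment for the WRAT4 premorbid measure taken from every patient

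*Combined protocol and SAP*

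**What the plan says.** Section 10.4 (repeating 7.4) lists endpoint II as "Amyloid plaque burden using regional semi-quantitative determinations is associated with greater objective cognitive impairment" and endpoint III as "Those individuals with the most profound cognitive impairment may have associated regional FDG metabolic changes consistent with neuronal loss or damage". Neither section defines objective impairment by a cut-off, norm, composite or reference level.

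The analysis of imaging against cognition, also in 10.4, is that the Z scores "can then be correlated with the various neuropsychological variables and clinical variables obtained to assess for differences and trends". For methods, "The data will be analyzed descriptively using summary statistics and paired t-tests", and Pearson correlations are named for pairs of imaging parameters. No regression, partial correlation or other covariate adjustment is mentioned.

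Section 9.3 (and 2.2) states that "the Wide Range Achievement Test (WRAT4) will be used to assess premorbid intellect in all participants". The WRAT4 does not appear again.

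Appendix D has a single neuropsychological testing column, and its footnote says that "The research MRI study and neuropsychological testing can be completed depending on staff availability", in any order relative to the PET sessions. Under 8.3, chemotherapy must have ended more than 6 and no more than 36 months before the first scan. Entry rests on self-report, "defined as being one or more standard deviations above normative data on our two scales of subjective cognitive dysfunction", so objective performance at entry is free to vary.

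**The concern.** A single post-chemotherapy score is a level, not a loss. A woman of high lifelong ability who has declined to average looks unimpaired, while a woman whose scores were always low ranks among the most impaired. Age norms, which the plan does not mention for these tests, would not remove that difference.

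Endpoints II and III depend on ordering patients by impairment. If part of the ordering reflects premorbid ability, there are two possible consequences:

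- If premorbid ability is unrelated to imaging, it adds noise and weakens a real relation.
- If premorbid ability is related to amyloid or metabolism, the unadjusted correlation is shifted as well.

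The protocol is alert to the issue elsewhere. Section 2.1 faults an earlier longitudinal study for having no baseline and reports impairment in 35% and 33% of patients before chemotherapy in two cited studies. Table 2 lists a flutemetamol study whose title concerns premorbid intellect. The results are meant to support a grant application (1.3), so it matters which associations look promising.

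**Working it through.** **The plan's own figure.** No power is stated for endpoints II and III. The only stated figure is for the primary test in 10.5: 12 patients, null rate 12%, alternative 42%, reject at 4 or more positives. The exact binomial gives P(X ≥ 4 | 12, 0.12) = 0.046 and P(X ≥ 4 | 12, 0.42) = 0.815. This agrees with the stated one-sided 0.05 and 80%. Nothing below changes it.

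**Inputs.** n = 12 (10.5). The rest are assumptions, because the documents give no correlations:

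- ρ, the correlation of WRAT4 with a test score: 0.4 to 0.6.
- The unadjusted imaging–score correlation: 0.50 in size.
- b, the correlation of WRAT4 with amyloid: 0 for dilution, −0.2 to −0.3 for bias.

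**Dilution (b = 0).** The partial correlation is r/√(1 − ρ²). Two-sided 5% power by Fisher z is Φ(atanh(r)·√(n − 3 − k) − 1.96), where k is the number of covariates. Unadjusted: atanh(0.50) × √9 = 1.648, so power is 37.8%. With k = 1 the multiplier is √8. The last two columns show a simple difference between standardised score and WRAT4, for which r becomes r/√(2(1 − ρ)) with k = 0.

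| ρ | ρ² | partial r | power | difference r | power |
|---|---|---|---|---|---|
| 0.4 | 16% | 0.546 | 40.9% | 0.456 | 31.5% |
| 0.5 | 25% | 0.577 | 46.1% | 0.500 | 37.8% |
| 0.6 | 36% | 0.625 | 54.5% | 0.559 | 47.4% |

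The partial correlation gains throughout the range. The simple difference loses at ρ = 0.4, breaks even at 0.5 and gains less at 0.6, because it forces a slope of 1 on WRAT4.

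**Bias (b ≠ 0, no true relation between imaging and decline).** The unadjusted correlation is ρb: from 0.4 × (−0.2) = −0.08 to 0.6 × (−0.3) = −0.18. The simple difference gives −b√((1 − ρ)/2): from 0.2 × √0.2 = +0.09 to 0.3 × √0.3 = +0.16. It reverses the sign of the spurious correlation and does not remove it. The partial correlation is zero by construction.

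**Wider range, by simulation** (200,000 replicates, n = 12). With score–premorbid correlations of 0.3 to 0.7, imaging–premorbid correlations of 0 to 0.5 and no true relation, the two-sided false-positive rate of the unadjusted correlation runs from 5% to 20% (7.4% at 0.5 and 0.3; 12.2% at 0.5 and 0.5). After partialling it is 5% throughout. With no imaging–premorbid link and a true imaging–decline correlation of 0.6, unadjusted power is 53%, 43% and 29% for score–premorbid correlations of 0.3, 0.5 and 0.7, against about 54% adjusted.

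**Cost.** The critical correlation is t/√(df + t²). With df = 10, t = 2.228 and r = 0.576; with df = 9, t = 2.262 and r = 0.602. The correlation detectable with 80% power moves from tanh(2.802/√9) = 0.73 to tanh(2.802/√8) = 0.76.

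**The case against.** The strongest reply is that these are exploratory endpoints in a 12-patient pilot, analysed descriptively with no stated test or power target, and that every correlation above is assumed. At the low end the gain is three points of power. WRAT4 is itself measured after chemotherapy, so adjusting for it still does not measure loss. All of this stands, and it limits the severity.

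A reader might infer that the plan misreads lifelong ability as chemotherapy damage. The documents do not support that. Endpoints II and III speak of objective impairment without attributing test scores to chemotherapy, and the term is left undefined; nowhere does the plan say that raw levels define it. Bias also needs a link between premorbid ability and imaging. The only hint of one is a study title in Table 2, which gives neither direction nor size. Without that link the harm is dilution.

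Nor is the WRAT4 excluded. It belongs to the battery in 9.3 and could count among the neuropsychological variables that 10.4 correlates with imaging. Being one more correlate is not adjustment, however, and no section of the plan supplies one.

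**Conclusion.** The point holds as a minor improvement. A premorbid measure is collected from everyone and given no stated analytic role, while two endpoints rest on an undefined impairment measured once, with no pre-chemotherapy baseline. On assumed WRAT4–score correlations of 0.4 to 0.6 and no WRAT4–amyloid link, adjustment recovers a modest amount of power. If such a link exists at −0.2 to −0.3, it removes a spurious correlation of −0.08 to −0.18. Even adjusted, 12 patients can reliably detect only correlations of about 0.76, so the endpoints stay exploratory. The primary binomial test, its sample size and its power are not touched.

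**What to change.** In 10.4:

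- Define objective impairment for endpoints II and III as performance relative to the WRAT4-predicted level, that is, the residual from a regression of each normed test score on WRAT4, with timed tests signed so that higher is better. Do not use a simple score-minus-WRAT4 difference.
- Report WRAT4-adjusted partial correlations with confidence intervals beside the unadjusted ones.
- Use the residual to identify the most profound impairment in endpoint III.
- State as a limitation that WRAT4, taken after chemotherapy, does not replace a true baseline. If the regression is fitted in these 12 patients, the residual ranks them against one another and does not show absolute impairment.

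The cost is a few sentences and one degree of freedom. No new data or visits are needed.
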